#### 8.1.2 Secondary endpoints

The secondary endpoints include:

- the distribution of the reasons that were considered relevant by the attending physician to take the decision indicated as primary endpoint;
- the rate of thromboembolic complications and the combined rate of bleeding requiring at least an interview with the attending physician (major or clinically relevant non-major bleeding), or death from any cause during the 2-year follow-up.

#### 8.1.3 Considerations on the study design

This is an observational study. As such, it allows collecting information based on the usual clinical practice as performed in the day-to-day clinical care of the target subjects.

However, as any investigator-initiated observational study, it may have a bias associated with the propensity of the individual investigator to participate in non-sponsored studies, with the local availability of personnel and time to collect and enter data, and with the investigator's willingness and capability to ensure an appropriate quality assurance on the collected data.

As in any clinical trial, furthermore, the need to obtain the written informed consent to data collection may also introduce a bias, which will probably select the more educated segment of the potential participants and, in any case, is likely to affect the consecutiveness of recruited cases.

## 8.2 Study set-up

### 8.2.1 Eligibility

Approximately 3,200 subjects will be enrolled. Each center will recruit not more than 40 among the consecutive subjects coming to the observation after approval of the protocol by the relevant EC/IRB until the total planned number of cases is overall collected. Consecutiveness may be replaced by other mean of bias containment if necessary given the center operational structure (e.g., all consecutive subjects reporting each first week of the month, a definite day in the week, or similar provisions). The selected predefined modality of screening and including patients should be declared by the participant centers. The subjects shall be able and willing to issue the informed consent to confer their data. Male and female adult and elderly subjects of any ethnicity, having had a first-ever event of DVT of the lower limbs and/or PE, treated with anticoagulants according to the local procedures but for not less than 3 and not more than 12 months, and having reached the final decision point on the therapy, are eligible to enter the study.

### 8.2.2 Inclusion criteria

Subjects meeting all of the following criteria qualify for entry into the study:

- a) subjects who provided a written informed consent and authorization for disclosure of protected health information;
- b) male and female adult or elderly subjects ( $\geq 18$  years at the time of signing the informed consent; no upper limit);
- c) of any ethnicity;
- d) with a first-ever event of provoked or unprovoked DVT of the lower limbs and/or PE treated with anticoagulants (NOACs, VKAs, or LMWHs) according to the local procedures (usually for 3 to 12 months) and to be re-evaluated to decide the treatment to be prescribed after this period;
- e) for whom the center possesses all the data relevant to the index event;
- f) having a permanent reference contact.

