Number of patients	A minimum number of 3,200 subjects will be enrolled across all the countries participating to the study, split into: approximately 200 subjects in China approximately 350 subjects in Czechia; approximately 300 subjects in Mexico; approximately 900 subjects in Poland; approximately 350 subjects in Portugal; approximately 250 subjects in Romania; approximately 800 subjects in Russia; approximately 150 subjects in Slovakia; not less than 100 subjects in Tunisia.
Period of enrolment	Not more than eighteen months
Period of follow-up	Two years
Inclusion criteria	
 
a) subjects who provided a written informed consent and authorization for disclosure of protected health information;
 
b) male and female adult or elderly patients (<math>\geq 18</math> years at the time of signing the informed consent; no upper limit) of any ethnicity having had a first-ever event of provoked or unprovoked DVT of the lower limbs and/or PE given maintenance anticoagulants (NOACs, VKAs, or LMWHs) according to the local procedures (usually for 3 to 12 months) and to be re-evaluated to decide the treatment to be prescribed after such period;
 
c) for whom the center is in possession of all the data relevant to the index event;
 
d) having a permanent reference contact.
 

Exclusion criteria	
 
a) subjects <math>< 18</math> years old;
 
b) subjects unable or unwilling to issue the written informed consent;
 
c) subjects for whom the information relevant to the index event are incomplete or inaccessible to the Investigator;
 
d) subject in whom the index event was a DVT not of the lower limbs;
 
e) subjects with life expectancy of less than 2 years;
 
f) subjects participating in any other clinical study, regardless of its nature;
 
g) subjects considered, by the attending physician, unable to comply with the study procedures.
 

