### 7.2 Objectives

#### 7.2.1 Primary objective

The primary objective of the study is the assessment of the distribution of decisions on the modality to manage the secondary prevention of venous thromboembolism (VTE), at the end of the period of anticoagulation considered standard. This period, initiated after the index event and defined in the present protocol as maintenance anticoagulation, ranges from the end of the 3rd month to the end 12th month. The anticoagulant used for the maintenance anticoagulation may or may not be the same used in the initial acute phase of VTE management (the initial 7 days). To the effect of this study, the treatment applied during the acute phase is of no interest.

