### 8.2.3 Exclusion criteria

Subjects meeting any of the following criteria will not qualify for entry into the study:

- a) subjects  $< 18$  years old at the time of consent request;
- b) subjects unable or unwilling to issue the written informed consent;
- c) subjects for whom the information relevant to the index event are incomplete or inaccessible to the Investigator;
- d) subject in whom the index event was a DVT not of the lower limbs;
- e) subjects with life expectancy of less than 2 years;
- f) subjects participating in any other clinical study, regardless of its nature;
- g) subjects considered, by the attending physician, unable to comply with the study procedures.

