#### **1. Enrollment and baseline visit**

The enrollment and baseline visit is the normally planned visit in which the physician has to decide on the continuation of the secondary prophylaxis after a first-ever thromboembolic episode treated for an appropriate period with anticoagulants. Due to organizational reasons, the enrollment and baseline visit may occur after the conclusion of anticoagulation. The time interval between conclusion of anticoagulation and enrollment visit should not exceed one month.

At the enrollment visit, all candidate subjects will receive an information sheet explaining design and aims of the study. The clinician shall explain and ask the subject to sign the informed consent form to confer the study data. The consent will also include the subject's agreement to receive regular phone calls from the investigator during the follow-up and to report annually to the center. The consent form will be part of the center documents and the only information conferred to the database will be whether the consent was signed or not, and in which date. The investigator will be responsible to archive the signed form for possible verification.

Subsequently, the investigator will:

- verify the inclusion/exclusion criteria for entering the study;
- inform by fax/mail the study Promoter that a new subject has been enrolled according to the protocol (form in Appendix III);
- obtain the information on the index event;
- monitor the clinical condition of veins and record the Villalta score;
- record the vascular risk factor, the concurrent diseases and the medications on long-term use;
- record the minimum clinical information required (weight, height, blood creatinine) as available; for creatinine, the last known serum creatinine level not older than three months before entering the study is appropriate;
- record the maintenance anticoagulation treatment received;
- decide on the subsequent subject's management and record the decision; the decision should be taken in the exclusive subject's interest and based exclusively on the personal judgment and in accordance with the local procedures;
- record the new form of management, if any;
- record the reasons influencing the decision taken;

- instruct the subject on the procedures of the follow-up, which should be the normal procedures in use at the center;
- provide a contact reference and obtain a contact reference.

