## Appendix IV – CRF template

### BASELINE FORM 1/8

#### Identification

Centre:  _ _ _  (from system based on user/ password)	Consecutive number in the centre:  _ _ _  ID (from system)  _ _ _ _ _ _ _	
NOTE: if >40 issue warning		
Date of this visit (dd/mm/yyyy):  _ _ / _ _ / _ _ _		
Informed consent signed:  0-no [STOP] 1-yes	Consent date (dd/mm/yyyy):  _ _ / _ _ / _ _ _  [consent date must be <= date of visit]	
Date of birth:  _ _ / _ _ / _ _ _  (dd/mm/yyyy)	Age:  _ _ _  [computed by system; consent minus birth; must be >=18 years]	
Ethnicity:  1-White 2-Black 3-Asian 4-Latino 5-Native American (both North and South) 6-Arabic 7-Other (specify) 9-N/A	Specification: ..... [if Ethnicity=7]	Sex:  0-Female 1-Male 9-N/A

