#### Index episode of venous thromboembolism

Date of diagnosis:  _ _ / _ _ / _ _ _  (dd/mm/yyyy) [must be 90-360 days before consent]	Type of event:  (only one option among: 1=proximal or proximal plus distal DVT of lower limbs 2=isolated distal DVT of lower limbs 3=DVT of lower limbs plus pulmonary embolism 4=pulmonary embolism without deep vein thrombosis
--	---

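### Section 8.2.1 fixes prior anticoagulation at 3 to 12 months, but the criteria lists say only 'usually', and the e-CRF date rule cannot accommodate a full 12-month course

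*Combined protocol and SAP*

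**What the plan says.** Three places in the protocol state who qualifies by length of prior treatment, and a fourth sets a data-entry rule.

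- Section 8.2.1 (Eligibility) is firm: subjects must have been "treated with anticoagulants according to the local procedures but for not less than 3 and not more than 12 months".
- Section 8.2.2 d) is descriptive: "treated with anticoagulants (NOACs, VKAs, or LMWHs) according to the local procedures (usually for 3 to 12 months". Criterion b) in the synopsis uses the same softening: "according to the local procedures (usually for 3 to 12 months".
- Section 8.2.3 opens with "Subjects meeting any of the following criteria will not qualify for entry into the study" and lists seven items, a) to g). None concerns duration of anticoagulation.
- Appendix IV, baseline form, says of the date of the index diagnosis that it "must be 90-360 days before consent".

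Two other statements matter. Section 7.2.1 defines the maintenance period, whose end is the moment of the primary endpoint, as one that "ranges from the end of the 3rd month to the end 12th month". Section 8.3.1 lets the enrolment visit follow the end of treatment: "The time interval between conclusion of anticoagulation and enrollment visit should not exceed one month".

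**The concern.** Section 8.3.1 tells the investigator to verify the inclusion and exclusion criteria, and section 8.2.2 says that subjects who meet all its items qualify. The limit that defines the target population is not in those lists. A center working from the lists can enrol a subject whom 8.2.1 excludes, and the Steering Committee, which classifies deviations under section 11.1 d), then has two standards to judge against.

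The e-CRF rule is the only numerical check on this point in the available text. It measures time from diagnosis to consent and not treatment duration, and it leaves no room for the gap that 8.3.1 permits. The subjects at risk are those at the end of month 12, which is the stated upper boundary of the primary-endpoint period. The stake is a consistent definition of who enters the primary analysis across nine countries.

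**Working it through.** **Inputs**

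- Eligible treatment duration: 3 to 12 months (section 8.2.1).
- Gap from end of treatment to enrolment: 0 to 1 month (section 8.3.1).
- e-CRF window, diagnosis to consent: 90 to 360 days (Appendix IV).
- Assumption: treatment starts on the day of diagnosis. The documents do not state this. A later start lengthens the interval for a given course and worsens the upper misfit. Treatment begun on suspicion 5-6 days before the recorded diagnosis would remove the no-gap misfit.

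**Reproducing the plan's window**

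3 × 30 = 90 and 12 × 30 = 360. The window is therefore 3 to 12 months in 30-day months with no gap.

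**Calendar lengths over all start dates in a four-year span**

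| Period | Days |
|---|---|
| 1 month | 28-31 |
| 3 months | 89-92 |
| 12 months | 365-366 |
| 12 months plus 1 month | 393-397 |

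**Upper end** (interval = course + gap; the rule requires 360 or less)

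- Full 12-month course, no gap: 365 − 360 = 5 and 366 − 360 = 6 days over. No start date gives 360 or fewer.
- Full 12-month course, one-month gap: 393 − 360 = 33 and 397 − 360 = 37 days over.
- Longest course that passes: 360 days with no gap. With the full gap it is 360 − 31 = 329 to 360 − 28 = 332 days.

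**Lower end** (the rule requires 90 or more)

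- No gap: 90 days agrees with 3 calendar months (89-92 days) to within 2 days.
- Shortest course that passes with the full gap: 90 − 31 = 59 to 90 − 28 = 62 days.
- An 80-day course needs a gap of at least 90 − 80 = 10 days, and a 70-day course at least 90 − 70 = 20 days.

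The rule is thus too tight at the upper end in every case of a full 12-month course. At the lower end it is loose only when an early stop and a gap occur together.

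**Can a date window do the job alone?** No. To admit every eligible subject its upper limit must be at least 397 days. A 13-month course with same-day enrolment is also 393-397 days and would pass, so the duration itself has to be checked.

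**The case against.** The other side has good points, and several limit what can be claimed.

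- **The intent is readable.** In 8.2.2 d) 'usually' can be read as describing local practice, with the limit set under the Eligibility heading and repeated in 7.2.1. That is a fair reading, but it does not put the limit into the lists that are verified.
- **A reader might infer that the e-CRF refuses every 12-month subject.** The documents do not establish this. The rule is phrased as a requirement, as are the age and consent-date checks, while the center cap is only a warning: "NOTE: if >40 issue warning". But the consent item on the same form carries an explicit stop marker and the date rule carries none. A block is plausible, not stated.
- **A reader might also infer that blocked subjects would vanish from the Committee's sight.** Section 8.3.1 has the investigator notify the promoter of each enrolment by fax or mail, separately from the e-CRF, so a notified but blocked subject could be noticed. Section 11.1 b) lets the Committee propose amendments for practical difficulties.
- **A reader might infer that the rule fails equally at both ends.** It does not. Section 6.1 regards three months as essential in all cases, so a stop at 59-62 days followed by a near-maximum gap should be rare. Section 8.3.2 d) lists duration as a collected variable, so such a case should be identifiable. The form content under the maintenance-treatment heading is not in the available text, and a duration check there cannot be ruled out. It could close the lower end; it would not lift the 360-day limit.
- **The no-gap misfit is only 5-6 days.** The decision can be taken while the subject is still on treatment, so a 12-month subject seen about a week early passes. Section 8.3.1 allows the gap only for organizational reasons. This reduces the number affected but does not remove the contradiction for a subject seen on schedule.

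**Conclusion.** The point holds at low severity. The firm limit in 8.2.1 is missing from the criteria lists, and the e-CRF date rule, followed as written, fails a full 12-month course that 8.2.1 admits: by 5-6 days with no gap and by 33-37 days with the full gap, assuming treatment starts at diagnosis. The lower end is sound when there is no gap.

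A reader might go further and infer a biased primary distribution. The documents give neither the number of subjects near either boundary nor how their decisions differ, so no effect on the decision shares can be estimated; it is probably small. Sample size and power are unaffected, because the calculation in section 10.2 uses only the total number and the assumed shares.

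**What to change.** 1. In 8.2.2 d) and synopsis b), replace the 'usually' wording with the firm 3-month minimum and 12-month maximum of 8.2.1.
2. Base the e-CRF eligibility check on the recorded duration of maintenance anticoagulation, already a listed variable in section 8.3.2 d).
3. If the diagnosis-to-consent check is kept beside it, raise its upper limit to about 400 days (at least 397), and state in the template whether a failed check blocks entry or only warns.

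The cost is a small edit to two lists and one e-CRF rule. Section 5 describes this version as still subject to committee approval. Where a center has already been approved, the change needs an amendment submitted to its EC/IRB. With 3,200 subjects and at most 40 per center there are at least 3,200 / 40 = 80 centers, so early correction is cheaper. A few short-treated subjects would be refused, and subjects with a full 12-month course would clearly be admitted.

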### 8.2.3 Exclusion criteria

Subjects meeting any of the following criteria will not qualify for entry into the study:

- a) subjects  $< 18$  years old at the time of consent request;
- b) subjects unable or unwilling to issue the written informed consent;
- c) subjects for whom the information relevant to the index event are incomplete or inaccessible to the Investigator;
- d) subject in whom the index event was a DVT not of the lower limbs;
- e) subjects with life expectancy of less than 2 years;
- f) subjects participating in any other clinical study, regardless of its nature;
- g) subjects considered, by the attending physician, unable to comply with the study procedures.

### 8.2.4 Withdrawal from study

Each subject has the right to refuse to continue on study at any moment and without justifications. However, since the study data are the usual data that the investigator collects for the standard subject's care, "withdrawal" should be intended as retiring the consent to the collection of subject's data into the study database. Consequently, from the moment a subject withdraws from the study, subsequent

information should not be collected among the study data. On the contrary, unless specifically indicated by the subject, all data collected up to that point will be retained among the study data.

### ***8.2.5 Replacement***

As usual in observational studies, no replacement is planned for subjects who retire the consent to confer the study data.

## **8.3 Study procedures**

Being this an observational study, all the procedures, therapeutic decisions and clinical assessments will be performed according to the standard, country specific clinical practice for the management of this kind of subjects.

### ***8.3.1 Visits***

The study does not anticipate other visits than those normally planned in the diagnostic-therapeutic course of the considered subjects. The visits are those of the normal routine. The period of observation for each subject is that normally anticipated by the clinical practice. The informed consent to the collection of data will equally be obtained during the course of a routine visit.

#### **1. Enrollment and baseline visit**

The enrollment and baseline visit is the normally planned visit in which the physician has to decide on the continuation of the secondary prophylaxis after a first-ever thromboembolic episode treated for an appropriate period with anticoagulants. Due to organizational reasons, the enrollment and baseline visit may occur after the conclusion of anticoagulation. The time interval between conclusion of anticoagulation and enrollment visit should not exceed one month.

At the enrollment visit, all candidate subjects will receive an information sheet explaining design and aims of the study. The clinician shall explain and ask the subject to sign the informed consent form to confer the study data. The consent will also include the subject's agreement to receive regular phone calls from the investigator during the follow-up and to report annually to the center. The consent form will be part of the center documents and the only information conferred to the database will be whether the consent was signed or not, and in which date. The investigator will be responsible to archive the signed form for possible verification.

Subsequently, the investigator will:

- verify the inclusion/exclusion criteria for entering the study;
- inform by fax/mail the study Promoter that a new subject has been enrolled according to the protocol (form in Appendix III);
- obtain the information on the index event;
- monitor the clinical condition of veins and record the Villalta score;
- record the vascular risk factor, the concurrent diseases and the medications on long-term use;
- record the minimum clinical information required (weight, height, blood creatinine) as available; for creatinine, the last known serum creatinine level not older than three months before entering the study is appropriate;
- record the maintenance anticoagulation treatment received;
- decide on the subsequent subject's management and record the decision; the decision should be taken in the exclusive subject's interest and based exclusively on the personal judgment and in accordance with the local procedures;
- record the new form of management, if any;
- record the reasons influencing the decision taken;

- instruct the subject on the procedures of the follow-up, which should be the normal procedures in use at the center;
- provide a contact reference and obtain a contact reference.

## **2. Follow-up visit**

The normal procedures for the long-term follow-up of these subjects include a number of calls – in general every 3 to 6 months – and a yearly recall at the center for a personal interview. The anticipated number of follow-up contacts is of approximately 4 to 8 calls and 2 interviews at the center, over the 2-year observation.

The information collected at calls and interviews are the usual ones used to monitor the status of the subject, and include:

- a. survival status;
- b. hospitalizations;
- c. thromboembolic complications;
- d. bleeding complications;
- e. review of the prophylactic treatment, if any was prescribed, and relevant changes if deemed necessary;
- f. other events that prevent the continuation of the planned follow-up.

## **3. Unplanned follow-up visit**

Upon request of the subject, or by decision of the investigator based on the communications with the subject, there may be the need for unplanned follow-up interviews. This will usually occur when a thromboembolic complication or a bleeding complication or other events occurred, that make clinically relevant for the well-being of the subject a direct contact with the investigator.

The information to be collected at these visits is the same as that of the follow-up visit. Usually, these visits imply the conclusion of the follow-up on the individual subject.

The follow-up is to be concluded, filling the end-of-study form discussed below, when:

- a. a thromboembolic complication occurred;
- b. a major bleeding complication occurred. Clinically relevant non-major bleedings as well as minor bleedings do not automatically imply the interruption of the follow-up and the relevant decision will be taken by the investigator case by case on the best subject's interest;
- c. there was a substantial change in anti-thrombotic therapy, such as:
  - institution, by the investigator or another physician, of a prophylactic therapy in a subject for whom the decision was taken not to continue the pharmacological prophylaxis;
  - replacement, by the investigator or another physician, of the current therapy with a new therapy of another therapeutic class. Changes of dosage of the same therapy do not imply interruption of the follow-up;
  - interruption, by the investigator or another physician or by subject's spontaneous decision, of the prescribed prophylactic treatment;
- d. an event occurred, that implied the impossibility to continue a correct monitoring, e.g., a planned/unplanned intervention requiring prolonged anticoagulation (e.g., surgery or immobilization).

